#### **13.8** Minority Accrual

Enrollment will be open to all eligible patients, regardless of race or ethnicity. There is no information currently available regarding differential effects of oxybutynin by race or ethnicity, and there is no reason to expect such differences to exist. Therefore, although the planned analysis will, as always, look for differences in treatment effect based on race and ethnicity, the sample size is not increased in order to provide additional power for subset analyses. However, it is well known that the incidence of prostate cancer is greater in African American men. Given this, an Alliance Health Disparities Committee member was added as a study co-chair to

facilitate appropriate accrual of minority patients. Efforts will be made to accrue a substantial number of African American men to this trial.

Based on prior Alliance studies involving similar disease sites, expected sizes of racial and ethnic subsets for patients registered to this study are shown in the following table:

#### 13.9 Inclusion of Minorities

PLANNED ENROLLMENT REPORT					
-		Ethni	c Categories		
Racial Categories	Not Hispanic or Latino		Hispar	Hispanic or Latino	
	Female	Male	Female	Male	
American Indian/ Alaska Native	0	1	0	0	1
Asian	0	1	0	0	1
Native Hawaiian or Other Pacific Islander	0	1	0	0	1
Black or African American	0	9	0	0	9
White	0	70	0	4	74
More Than One Race	0	1	0	0	1
Total	0	83	0	4	87

Ethnic Categories:

- Hispanic or Latino a person of Cuban, Mexican, Puerto Rican, South or Central American, or other Spanish culture or origin, regardless of race. The term "Spanish origin" can also be used in addition to "Hispanic or Latino."
- Not Hispanic or Latino

Racial Categories:

- American Indian or Alaskan Native a person having origins in any of the original peoples of North, Central, or South America, and who maintains tribal affiliations or community attachment.
- Asian a person having origins in any of the original peoples of the Far East, Southeast Asia, or the Indian subcontinent including, for example, Cambodia, China, India, Japan, Korea, Malaysia, Pakistan, the Philippine Islands, Thailand, and Vietnam. (Note: Individuals from the Philippine Islands have been recorded as Pacific Islanders in previous data collection strategies.)
- Black or African American a person having origins in any of the black racial groups of Africa.
- Native Hawaiian or other Pacific Islander a person having origins in any of the original peoples of Hawaii, Guam, Samoa, or other Pacific Islands.
- White a person having origins in any of the original peoples of Europe, the Middle East, or North Africa.

#### 14.0 GENERAL REGULATORY CONSIDERATIONS AND CREDENTIALING

#### **14.1 Limited Access Requirements**

Institutions that are interested in participating in this study must be able to rebottle liquid formulation of drug and placebo into patient specific supplies. In order for the Alliance to monitor starter supply distribution, institutions are asked to document their commitment to the requirements of the study as follows:

- In order for a site to be considered for the study, a "Site Participation Form" must be completed. The form can be requested from and once completed returned to
- Upon approval, the site will be added to the list of limited access institutions with the next update to this protocol.

Sites will receive extra per patient reimbursement for the effort involved with rebottling liquid formulations of the drug.

#### **15.0 MONITORING PLAN**

Use standard Alliance monitoring procedures, including regular review by the Alliance Data Safety Monitoring Board (DSMB) as outlined in Section 13.7.

#### APPENDIX I HOT FLASH DEFINITIONS FOR THE MALE PATIENT

#### **Patient Information Sheet**

Please refer to these examples of hot flashes that have been given by cancer survivors in previous studies when describing their hot flash severity. One or more of these descriptions may help to categorize your hot flash as mild, moderate, severe, or very severe.

#### MILD

Duration: Lasting less than 3 minutes

Physical symptoms: Very light perspiration, generalized warmth or a flushed sensation

Emotional symptoms: None or rare

Action needed: Usually no action taken

#### **MODERATE**

Duration: Lasting up to 5 minutes

Physical symptoms: Light-to-moderate perspiration, moderate warmth and/or perspiration

Emotional symptoms: Mild anxiety, some irritability, loss of concentration

Action needed: Needed to use a fan, needed to loosen clothing, needed to remove clothing, needed to remove bedding

#### SEVERE

Duration: Lasting up to 10 minutes

Physical symptoms: Described as feeling "hotter" or "very hot," heavy perspiration, dizziness, nausea, shortness of breath, weakness, extreme discomfort

Emotional symptoms: Moderate anxiety, moderate irritability

Action needed: Needed to loosen clothing, needed to change clothing, needed to change bedding

#### VERY SEVERE

Duration: Lasting up to 30 minutes

Physical symptoms: Described as feeling "very hot," drenching perspiration, dizziness, nausea, shortness of breath, weakness, chest discomfort, extreme discomfort

Emotional symptoms: Severe anxiety, severe irritability, restlessness, totally out of control

Action needed: Needed to change clothing, needed to towel off, needed to change bedding, used wet towels, took a bath or shower, needed a rest

#### APPENDIX II BASELINE SYMPTOM DOCUMENTATION

#### **Directions:**

- The baseline symptom determination is divided into 7 rows, one for each day of the week.
- Enter the day and the date your week started.
- Start in the row for Day 1.
- Write in the number of mild, moderate, severe and very severe hot flashes experienced in the boxes.
- Repeat for each day of the week.
- See page 2 of this booklet for the definitions of each type of hot flashes.

Day week started:	Date week started:	/	/ /	/			
		m m	$\overline{d} d$	$\overline{y}$	y	$\overline{y}$	$\overline{y}$

Day	Number of mild hot flashes	Number of moderate hot flashes	Number of severe hot flashes	Number of very severe hot flashes
Day 1				
Day 2				
Day 3				
Day 4				
Day 5				
Day 6				
Day 7				

\*A day should be considered a 24-hour period (i.e. 7 a.m. to 7 a.m. or midnight to midnight).

#### APPENDIX III INTERNATIONAL PROSTATE SYMPTOM SCORE (IPSS)

#### (To be completed at screening and at the end of each week of treatment)

#### INTERNATIONAL-PROSTATE SYMPTOM SCORE

Question	Not at all	Less than 1 time in 5	Less than half the time	About half the time	More than half the time	Almost always
1. Over the past week, how often have you had a sensation of not emptying your bladder completely after you finished urinating?	0	1	2	3	4	5
2. Over the past week, how often have you had to urinate again less than two hours after you finished urinating?	0	1	2	3	4	5
3. Over the past week, how often have you found you stopped and started again several times when you urinated?	0	1	2	3	4	5
4. Over the past week, how often have you found it difficult to postpone urination?	0	1	2	3	4	5
5. Over the past week, how often have you had a weak urinary stream?	0	1	2	3	4	5
6. Over the past week, how often have you had to push or strain to begin urination?	0	1	2	3	4	5
	None	1 time	2 times	3 times	4 times	5 or more times
7. Over the past week, how many times did you most typically get up to urinate from the time you went to bed at night until the time you got up in the morning?	0	1	2	3	4	5

I-PSS - United States/English ID 5070 / I-PSS1a\_AU1.0\_eng-USori.doc

#### INTERNATIONAL-PROSTATE SYMPTOM SCORE (cont'd)

#### QUALITY OF LIFE DUE TO URINARY SYMPTOMS

Question	Delighted	Pleased	Mostly satisfied	Mixed about equally satisfied and dissatisfied	Mostly dissatisfied	Unhappy	Terrible
1. If you were to spend the rest of your life with your urinary condition just the way it is now, how would you feel about that?	0	1	2	3	4	5	6

I-PSS - United States/English ID 5070 / I-PSS1a\_AU1.0\_eng-USori.doc

#### APPENDIX IV HOT FLASH DIARY (SAMPLE INCLUDED ON THE NEXT PAGE)

#### **Directions:**

The hot flash diary is divided into 7 rows, one for each day\* of the week. Enter the day and the date your week started. Start in the row for Day 1. Write in the number of mild, moderate, severe and very severe hot flashes experienced in the boxes. Repeat for each day of the week.

See page 2 of this booklet for the definitions of each type of hot flashes.

Day week started: \_\_\_\_\_ Date week started: \_\_\_\_\_  $/ \frac{d}{d} / \frac{y}{y} \frac{y}{y} \frac{y}{y} \frac{y}{y}$ 

Day	Number of mild hot flashes	Number of moderate hot flashes	Number of severe hot flashes	Number of very severe hot flashes	How many doses of study medication did you take? (circle one)
Day 1					0 1 2
Day 2					0 1 2
Day 3					0 1 2
Day 4					0 1 2
Day 5					0 1 2
Day 6					0 1 2
Day 7					0 1 2

\*A day should be considered a 24-hour period (i.e. 7 a.m. to 7 a.m. or midnight to midnight).

mm dd

yyyy

#### Directions:

The hot flash diary is divided into 7 rows, one for each day of your week. Enter the day and the date your week started. Start in the row for Day 1. Write in the number of mild, moderate, severe and very severe hot flashes experienced in the boxes. Repeat for each day of the week. See page 2 of this booklet for the definitions of each type of Hot Flashes.

#### Example:

Day week started:	Friday	Date week started:	9/	2/	2016
-------------------	--------	--------------------	----	----	------

Day	Number of mild hot flashes	Number of moderate hot flashes	Number of severe hot flashes	Number of very severe hot flashes	How many doses did you take today? (circle one)
Day 1	3	2	1	0	0 1 2
Day 2	7	3	0	0	01 2
Day 3	6	0	1	2	0 1 2
Day 4	2	1	0	0	0 1 2
Day 5	3	3	1	1	0 1 2
Day 6	2	1	0	0	0 1 2
Day 7	5	2	2	0	0 1 2

#### **APPENDIX V SYMPTOM EXPERIENCE QUESTIONNAIRE**

#### Completed at baseline and weekly for six weeks

Date completed: INSTRUCTIONS: Please complete at the end of each study week by circling the one number for each item below that best describes you. 1. Over the past week, have you experienced stomach pain or cramps? Not As bad as it can be at all 2. Over the past week, have you experienced diarrhea (loose stools)? Not As bad as at all it can be 3. Over the past week, have you experienced constipation? Not As bad as it can be at all 4. Over the past week, have you experienced nausea? Not As bad as it can be at all 5. Over the past week, have you experienced any vomiting? Not at As bad as it all can be 6. Over the past week, have you experienced dry mouth? Not As bad as it can be at all

7.	Over the pas	st week,	, have yo	ou experi	ienced di	zziness?	,				
	0 Not at all	1	2	3	4	5	6	7	8	9	10 As bad as it can be
8.	Over the pas	st week,	, have yo	ou experi	ienced de	ecrease in	n appetit	te?			
	0 Not at all	1	2	3	4	5	6	7	8	9	10 As bad as it can be
9.	Over the pas	st week,	, have yo	ou experi	ienced he	eadaches	?				
	0 Not at all	1	2	3	4	5	6	7	8	9	10 As bad as it can be
10.	Over the pas	st week,	, have yo	ou experi	ienced fa	tigue?					
	0 Not at all	1	2	3	4	5	6	7	8	9	10 As bad as it can be
11.	Over the pas	st week,	, have yo	ou experi	ienced ex	cessive	somnole	ence (sle	epiness)?	2	
	0 Not at all	1	2	3	4	5	6	7	8	9	10 As bad as it can be
12.	Over the pas	st week,	, have yo	ou experi	ienced bl	urry visi	ion?				
	0 Not at all	1	2	3	4	5	6	7	8	9	10 As bad as it can be
13.	Over the pas	st week,	, have yo	ou experi	ienced dı	y eyes?					
	0 Not at all	1	2	3	4	5	6	7	8	9	10 As bad as it can be

14. Over the past week, have you experienced episodes of confusion?

		0 Not at all	1	2	3	4	5	6	7	8	9	10 As bad as it can be
15.	Over	the past	week, ha	ave you l	had a ski	in rash?						
		0 Not at all	1	2	3	4	5	6	7	8	9	10 As bad as it can be
16.	Over	the past	week, di	id you ex	perience	e any mu	scle/join	t aches o	or pains?			
		0 Not at all	1	2	3	4	5	6	7	8	9	10 As bad as it can be
17.	Over	the past	week, di	id you ex	perience	e trouble	sleeping	?				
		0 Not at all	1	2	3	4	5	6	7	8	9	10 As bad as it can be
18.	18. Over the past week, have you had trouble concentrating?											
		0 Not at all	1	2	3	4	5	6	7	8	9	10 As bad as it can be
19.	Over	the past	t week, l	nave you	ı experie	enced an	y difficu	ulties wi	th your :	memory	?	
		0 Not at all	1	2	3	4	5	6	7	8	9	10 As bad as it can be
20.	Over	the past	week, ha	ave you e	experien	ced diffi	culties u	rinating	(difficult	ties emp	tying you	ır bladder)?
		0 Not at all	1	2	3	4	5	6	7	8	9	10 As bad as it can be
21.	Over	the past	week, ha	ave you e	experien	ced any	trouble v	vith urin	e inconti	nence (le	eaking)?	
		0 Not at all	1	2	3	4	5	6	7	8	9	10 As bad as it can be

22. Over the past week, how distressing was your experience with hot flashes?

0	1	2	3	4	5	6	7	8	9	10
Not										As bad as
at all										it can be

23. Did you experience any other symptoms this past week that were not mentioned above?

NoYes

If so, please describe

#### The following question will ONLY be asked at baseline:

23a. How much do you think the study medication will be able to help hot flashes?

0	1	2	3	4	5	6	7	8	9	10
Probably won't work										Will work extremely well

#### The following question will NOT be asked at baseline:

23b. Over the past week, how satisfied are you with the control of your hot flashes?

0	1	2	3	4	5	6	7	8	9	10
Extremely Satisfied										Extremely Dissatisfied

23c Given your experience with the study medication on this trial would you want to continue it after the trial is over if given the choice?

NoYes

#### APPENDIX VI HOT FLASH RELATED DAILY INTERFERENCE SCALE (HFRDIS)

#### Completed on Day 7, at the end of Weeks 3, 5, and 7 (i.e., Days 21, 35, and 49

Please circle one number to the right of each phrase to describe how much DURING THE	
PAST TWO WEEKS hot flashes INTERFERED with each aspect of your life.	

		Did not								Completely			
1.	Work (work outside the home and housework)	0	1	2	3	4	5	6	7	8	9	10	
2.	Social activities (time spent with family, friends, etc)	0	1	2	3	4	5	6	7	8	9	10	
3.	Leisure activities (time spent relaxing, doing hobbies, etc.)	0	1	2	3	4	5	6	7	8	9	10	
4.	Sleep	0	1	2	3	4	5	6	7	8	9	10	
5.	Mood	0	1	2	3	4	5	6	7	8	9	10	
6.	Concentration	0	1	2	3	4	5	6	7	8	9	10	
7.	Relations with others	0	1	2	3	4	5	6	7	8	9	10	
8.	Sexuality	0	1	2	3	4	5	6	7	8	9	10	
9.	Enjoyment of life	0	1	2	3	4	5	6	7	8	9	10	
10	. Overall quality of life	0	1	2	3	4	5	6	7	8	9	10	

HFRDIS © 2001 [name]

#### APPENDIX VII NURSE/CRP PHONE CONTACT GUIDE

Patient Phone No.\_\_\_\_\_ Best Dates/Times to call\_\_\_\_\_

#### FOLLOW UP:

- 1. Please make an appointment to call the patient at home the end of each study week. The purpose of this contact is to remind the patient of dose schedule, document compliance, encourage completion of the booklet, and address problems.
  - It is important to reinforce daily completion of diary as well as weekly side effects on symptom experience questionnaire. Regarding potential side effects, please ask about dry mouth, nausea, vomiting, dizziness, blurred vision, dry eyes, urinary retention, and urinary incontinence. If there are any significant toxicities, then refer to protocol Section 8.2 for potential dose modifications. In addition, determine whether there are any reportable adverse events (Section 9.0).
- 2. Items to document on the Nurse/CRP Evaluation form in the forms packet include, but are not limited to the following:
  - Date of phone call
  - Study week
  - Side effects:
    - > Type of side effect, severity and attribution, if applicable
  - Any changes in medications or other treatments (i.e. behavioral, diet, etc.)
  - Has the participant taken the proper amount of study medication each day? (Choose one: Always\_\_\_\_, Usually\_\_\_\_\_, Rarely\_\_\_, or Never\_)
  - Questions/Comments
- 3. Reinforce compliance with study medication.
- 4. Reinforce completion of questionnaires and request return of them at end of weeks 1 and 4.

Note – If patient decides to stop study before week 7, ask them to fill out the questionnaires up to that point at the end of the booklet and return in the envelope provided.

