#### **1.2** Oxybutynin for Hot Flashes

Oxybutynin is an anti-cholinergic agent which is available in both oral and transdermal formulations. Currently, oxybutynin is approved by the Food and Drug Administration (FDA) for use in managing overactive bladder symptoms. Additionally there are randomized trial data supporting off label use for the management of hyperhidrosis, with studies showing that this effect is equal across both genders.[22-24] Oxybutynin has a very good safety profile, with the most common reported adverse effects being xerostomia, drowsiness, dizziness, mild cognitive effects, and urinary retention, which are typically mild in severity and resolve with discontinuation, if not tolerable.[25]

In 2007, a manuscript reported retrospective data that supported the efficacy of oxybutynin for managing refractory hot flash symptoms in 52 cancer patients, including four men with ADT-

induced hot flashes.[26] The promising results of this study, which suggested a 70% response rate to oxybutynin with acceptable toxicity, led to the development of Phase III, double-blind, randomized trials comparing oxybutynin to placebo in women with hot flashes.[27, 28] One such trial demonstrated that moderate doses of oxybutynin substantially decreased hot flashes with mild to moderate toxicity. [27] More recently, our group completed another study which compared oxybutynin at doses of 2.5 and 5.0 mg BID to placebo in women with symptomatic hot flashes. These results were presented as an oral abstract at the 2018 San Antonio Breast Cancer Symposium, and showed that hot flash scores were significantly reduced from baseline in both the 2.5 mg (-10.6, SD 7.7) and 5.0 mg (-16.9, SD 15.6) treatment arms compared to placebo (-5.7, SD 10.2). Additionally, hot flash frequency was significantly improved for patients receiving both dose levels of oxybutynin (2.5 mg=60% reduction, 5.0 mg=77% reduction) over those treated with placebo (27% reduction). Reported treatment-related adverse effects for participants were typically mild and there was no difference in the discontinuation of the study drug between the oxybutynin and placebo arms. [28]

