#### **1.3.4** Cognitive effects

One potential concern when using anti-cholinergic agents, such as oxybutynin, for extended periods is the potential negative impact on cognition via interaction with muscarinic receptors within the central nervous system. Prospective studies, conducted primarily in elderly patients with overactive bladder symptoms, have demonstrated conflicting findings with regard to the effects of oxybutynin on neuro-cognition relative to placebo.[37-40] Questions relating to patient-reported cognition will be asked via the Symptom Experience Questionnaire (Appendix V) at baseline and weekly during the 6-week treatment period to help ascertain the effects of oxybutynin relative to placebo. These data will ultimately provide insight regarding the potential for cognitive toxicity with oxybutynin, which can be useful when considering the therapeutic index of this medication for treating hot flashes.

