#### 9.1.1 Solicited adverse events

There are no additional solicited adverse events for this trial.

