#### Adverse Events

Consult the package insert for the most current and complete information.

Following administration of oxybutynin chloride, the following symptoms may occur:

Cardiovascular: Palpitations, tachycardia, vasodilatation

Dermatologic: Decreased sweating, rash

Gastrointestinal/Genitourinary: Constipation, decreased gastrointestinal motility, dry mouth, nausea, urinary hesitance and retention

Nervous System: Asthenia, dizziness, drowsiness, hallucinations, insomnia, restlessness

Ophthalmic: Amblyopia, cycloplegia, decreased lacrimation, mydriasis

Other: Impotence, suppression of lactation

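### The weekly call guide is the only scheduled staff adverse-event assessment, and its eight named prompts omit effects the protocol itself lists, so CTCAE capture is uneven, mainly at grade 2 and in crossover

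*Combined protocol and SAP*

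**What the plan says.** Section 5.0 has one calendar row for staff assessment of adverse events, the telephone contact at the end of each treatment week. Its second footnote and Section 11.6 carry the weekly calls into the unblinded crossover phase. No questionnaire is scheduled there.

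Appendix VII, item 1, tells the caller what to raise: "please ask about dry mouth, nausea, vomiting, dizziness, blurred vision, dry eyes, urinary retention, and urinary incontinence". The same bullet continues: "In addition, determine whether there are any reportable adverse events". Item 2 has the caller document "Type of side effect, severity and attribution, if applicable".

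Elsewhere the protocol describes the expected effects more widely:

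- Section 1.2 gives the most common as "xerostomia, drowsiness, dizziness, mild cognitive effects, and urinary retention".
- Section 1.3.4 devotes a subsection to "the potential negative impact on cognition via interaction with muscarinic receptors" and assigns its measurement to the Symptom Experience Questionnaire.
- Section 10.1 (Adverse Events) includes "Cardiovascular: Palpitations, tachycardia, vasodilatation" and "Nervous System: Asthenia, dizziness, drowsiness, hallucinations, insomnia, restlessness", and also constipation, decreased sweating and rash.

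Section 9.2 requires routine reporting of grade 2 events only when they are at least possibly related, and of grade 3 or higher events whatever the attribution. Grade 1 events are not reported routinely.

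**The concern.** A named prompt is put to every man every week. An effect without one reaches the CTCAE record only if the man volunteers it or the caller's open question happens to bring it out. If the prompt list does not match the effects the protocol expects, the CTCAE profile will be more complete for some expected effects than for others because of how they were asked about.

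At stake is Objective 2.2.2, the safety and adverse event profile of the two doses. The crossover phase is affected too: every man there takes oxybutynin, and Section 11.6 gives collection of adverse events as the purpose of its calls.

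**Working it through.** No sample-size or error-rate figure bears on this point. The check is a cross-match of lists.

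**Step 1: the most common effects (Section 1.2) against the call.** Dry mouth (xerostomia), dizziness and urinary retention are prompted. Drowsiness and cognitive effects are not. That is 3 of 5 prompted and 2 of 5 unprompted.

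**Step 2: the omitted effects against both instruments.** Questionnaire items are those in Appendix V.

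| Effect | Listed in | Named in call | Named questionnaire item |
|---|---|---|---|
| Drowsiness | 1.2, 10.1 | No | 11 |
| Cognitive effects | 1.2, 1.3.4 | No | 14, 18, 19 |
| Constipation | 10.1 | No | 3 |
| Rash | 10.1 | No | 15 |
| Palpitations, tachycardia | 10.1 | No | None |
| Hallucinations | 10.1 | No | None |
| Decreased sweating | 10.1 | No | None |

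Of these seven, four have a named weekly item in the blinded phase and three have none in either instrument. In crossover, where only the calls are scheduled, all seven lack a named prompt.

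**Step 3: does the questionnaire feed CTCAE?** Sections 13.3 and 13.4 use it for the tolerability endpoint, with a mixed model per symptom. No section tells staff to review its answers for grade or attribution. The timing of return also varies. Section 6.2 allows weekly mailing or return at a clinic visit, Section 11.1 asks for return after the baseline week and after week 7, and Appendix VII requests return at the end of weeks 1 and 4. An answer may therefore reach staff well after the event.

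**Step 4: what remains for the three effects with no named item?** There is the open check in the call, open item 23 of the questionnaire, and spontaneous report. The nursing guidelines in Section 10.1 tell patients to report palpitations or tachycardia. For decreased sweating and hallucinations they give warnings and advise caution, without an instruction to report. The medication diary (Appendix VIII) has a comments column for side effects but is marked as a convenience form.

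**Step 5: which grades are exposed?** Under Section 9.2, better elicitation can change the routine record at grade 2 (at least possibly related) and at grade 3 or higher. The stopping rule in Section 13.7.1 and the planned safety summary in Section 13.4 use grade 3 or higher only. Events of that severity are the least likely to pass a weekly call unmentioned, which leaves grade 2 as the main exposure.

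**Step 6: effect on the comparison of arms.** The guide is the same for all blinded arms. If the chance *s* of recording an event is equal across arms, the observed difference is s·p₁ − s·p₀ = s(p₁ − p₀). No difference is created; a true absolute difference is shrunk by the factor *s*. The documents give no value for *s*.

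**Step 7: scale.** 87 men × 6 weekly calls = 522 calls at most in the blinded phase. With 2:2:1:1 allocation the placebo arms hold 87 × 2/6 = 29 men, so crossover adds at most 29 × 6 = 174 calls. These figures count opportunities to ask; they do not measure events lost.

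**The case against.** The strongest reply is that the eight prompts are reminders added to an open enquiry. The same bullet requires the caller to look for any reportable event, and the form records any type of side effect. The questionnaire asks directly each week about constipation, somnolence, confusion, concentration and memory, and Section 1.3.4 assigns cognition to it by design. The Nurse/CRP Evaluation form is in a forms packet outside these documents, and Appendix VII says its contents are not limited to those shown, so it may hold further prompts.

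Much of this stands, and it rules out several stronger readings that a reader might infer:

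- *That drowsiness, cognitive effects, constipation, palpitations and decreased sweating are all under-captured.* Not supported. The first three are measured weekly in the blinded phase for the tolerability endpoint, and the other two have open routes.
- *That the safety comparison is biased between arms.* Not supported. The prompts are identical in the blinded arms.
- *That the stopping rule is compromised.* Not shown. It counts grade 3 or higher events.
- *That Section 9.1.1 contradicts the guide.* It says "There are no additional solicited adverse events for this trial". The word additional leaves room for prompts in a phone guide, and the sentence sits among the reporting rules, so no clear contradiction follows.

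What the reply does not answer is that questionnaire ratings have no stated path to CTCAE grading, that three listed effects have no named item in either instrument, and that crossover has the calls alone.

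**Conclusion.** The prompt list is out of line with the protocol's own account of expected effects. The consequence is CTCAE elicitation that is uneven, less sensitive and possibly later for the omitted effects, chiefly for grade 2 events at least possibly related to treatment and for men in crossover.

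The count of omissions is firm; the number of events affected cannot be derived. The conclusion rests on two assumptions: that named effects are reported more readily than unnamed ones, for which the documents give no source, and that the unseen evaluation form does not already supply the missing prompts. Because Section 13.4 plans a formal safety summary only at grade 3 or higher, the loss falls on the descriptive profile under Objective 2.2.2. This is an inexpensive improvement and does not threaten the trial's main conclusions.

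**What to change.** In Appendix VII, item 1, and on the Nurse/CRP Evaluation form if it does not already have them, add these prompts:

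- drowsiness
- confusion, memory problems or hallucinations
- constipation
- palpitations or fast heartbeat
- decreased sweating or overheating
- rash

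Use the same list in every arm and in the crossover calls. Add one sentence directing the caller to ask about symptoms marked on that week's questionnaire, so that they can be given a CTCAE grade and attribution.

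The cost is a few words in the guide, the matching form change and slightly longer existing calls. More low-grade reports will follow, prompted equally in all arms; under Section 9.2 the grade 1 ones need no routine submission. No endpoint, visit, dose or sample size changes.
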